3.4.3 Exploratory Efficacy End Point: Clinical Global Impression (CGI)

At each visit, the physician (Principal Investigator) will use his clinical evaluation (all signs and symptoms taken together) to provide a global assessment of the subjects' change in symptoms and signs. The CGI is as follows: ⁶²

Question (to physician): In general, compared with the subjects' symptoms and signs at baseline, how would you characterize his/ her overall signs and symptoms now?

The responses will be categorized on a seven point scale as follows:

Marked worsening

Moderate worsening
Minimal worsening
Unchanged
Minimal improvement
Moderate improvement
Marked improvement

3.4.4 Exploratory Efficacy End Point: Subject Global Assessment (SGA)

At each visit, the subjects will be asked to assess their overall change from baseline. The SGA is as follows:⁶²

Question 1 (to subject): Compared with your first visit, how are your eye symptoms now?

The responses will be categorized on a five point scale as follows:

Much worse
Worse
About the same
Improved
Much improved

Question 2 (to subject): Compared with your first visit, how is the mucous strings or mucous discharge from your eyes now?

[figure not shown]
The responses will be categorized on a five point scale as follows:

Much worse
Worse
About the same
Improved
Much improved

3.4.5 Exploratory Efficacy End Point: Ocular surface redness score

Ocular surface redness (nasal or temporal) will be assessed using the Validated Bulbar Redness grading scale (VBR).⁶³ The VBR consists of a set of ten images illustrating different degrees of ocular surface redness (OR), ranging from normal to severe, and each image is assigned a value in an order of ascending severity. Colored copies of these images will be made and put up in all the examination rooms. Subjects will be examined by a slit-lamp and the bulbar conjunctival injection of the subject's eye (nasal and temporal) will be compared to the reference images and graded accordingly.

Photographic anchors and their respective grades for ocular surface redness are shown below:

[figure not shown]

3.4.6 Exploratory Efficacy End Point: Keratograph Oculus Redness Score

Keratograph is FDA approved and is used in routine clinical care of patients in the US. The Oculus Keratograph 5M performs a non-invasive tear film analysis. It uses a Placido bowl with a camera aperture that has a fixation mark in the center. The device provides consistent illumination, allowing scanning of the exposed bulbar conjunctiva to take place. The keratograph then analyzes the scanned area. This system generates a BR score automatically, which is based on the area percentage ratio between the vessels and the rest of the analyzed area. For instance, if the ratio is 16%, then the score is 1.6. The maximum ratio, according to the manufacturer, is 40%; therefore, the BR scores that the machine generates range between 0.0 and 4.0.

Non-invasive Keratograph Tear Film Break-up Time (NIK BUT)

The non-invasive Keratograph tear film break-up time (NIK BUT) measures tear film stability. The NIK BUT is automatically measured within seconds, without fluorescein application. Tear Break-up Time (TBUT) will be measured twice for each eye using IR video derived from the Oculus noninvasive Keratograph tear breakup time (NIK BUT) tool. Based on the device IR video, the device generates 2 measures for TBUT: NIK BUT-first (time at which the first breakup of tears occurs) and NIK BUT-average (average time of all breakup incidents) automatically and without touching the eye.

3.4.7 Exploratory Efficacy End Point: InflammaDry for MMP-9 Protein

InflammaDry is FDA approved and is used in routine clinical care of patients in the US. Elevated levels of the MMP-9 protein in human tears will be detected visually, qualitatively, and in vitro using InflammaDry for MMP-9. InflammaDry will be performed PRIOR to instilling ocular anesthetic, topical dyes, or performing Schirmer testing. Tear fluid sample will be collected by gently dabbing the sampling fleece on the inside of the patient's palpebral conjunctiva. The test is assembled by gently placing the sampling fleece of the sample collector into the sample transfer window of the test cassette body. The buffer vial is opened and immersed in the absorbent tip. The absorbent tip is removed from the buffer vial, the protective cap is replaced, and the test is laid flat on a horizontal surface. The results of the test are indicated through two (2) lines, the control line and the result line in the result window.

POSITIVE RESULT: The presence of both a BLUE line in the control zone and a RED line in the result zone indicates a positive result. A positive result indicates the presence of MMP-9 ≥ 40 ng/ml.

NEGATIVE RESULT: The presence of only a BLUE line in the control zone indicates a negative result. A negative result is indicative of an MMP-9 < 40 ng/ml.

INVALID RESULT: If a BLUE line does not appear, the test may be invalid. Re-immerses the absorbent tip into the buffer vial for an additional ten (10) seconds. If a BLUE line still does not appear, the test must be discarded and the subject retested by resampling the eye using a new InflammaDry test.

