3.6 Other Study procedures: Ocular Surface Washings

At the first (Baseline) and last treatment (8 week) visits, ocular surface washings will be collected as follows: 50 μ L of artificial tear (Preservative Free Refresh Optive Sensitive, Allergan, Irvine, CA) was instilled into the lower fornix of the eye. The patient will be instructed to perform ductions in all directions, and after approximately 1 minute the conjunctival washings were collected with a 5 μ L glass microcapillary tube (Microcaps Drummond Scientific, Broomall, PA) and transferred to a sterile 0.2 mL microcentrifuge tube. The samples will be stored at cold temperature (approximately 4 degrees C) until further analysis. Ocular Surface washings will be transported to the laboratory and used for potential biomarker analysis etc.

4 Subject Selection and Withdrawal

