6.5.2 Visit 2 Day 1 (Randomization and First treatment visit)

Prior to first dose (Baseline)

- Record concomitant medications
 - Vital Signs: Blood pressure, Pulse, and Temperature taken while subject is in a sitting position.
 - Visual Acuity (Snellen’s chart) with eye glasses (if applicable)
 - OSDI
 - Symptom Intensity Assessment
 - Keratograph Oculus Redness Score
 - > Non-invasive Keratography Tear Film Break-up Time (NIK BUT)
 - Schirmer I test
 - Baseline Ophthalmic Examination (slit lamp examination, VBR)
 - Ocular surface wash collection for analysis (Potential biomarkers)
 - InflammADry Test for MMP-9 Protein
 - Lissamine Dye Corneal and Conjunctival staining
 - Adverse events since screening visit.
- ***Randomization (by pharmacy)***
 - ***Dispensing of study drug/placebo (by Pharmacy)***
 - ***Investigator/designee administers first dose of study drug/ placebo***

Post-Dose

- Test Substance Tolerance (Visual Analogue Scale; VAS)
- Subjects will be trained on how to self-administer the study eye drops and be given a sufficient supply to last for 4 weeks to take home.
- Subjects will receive a study diary on which to record the day/time of each dose and any adverse effects.
- Post dose evaluation for any adverse effects.
- Intraocular pressure measurement after topical anesthesia to eye

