6.5.4 Visit 4: Week 8 (\pm 4 days)

Treatment Visit (after any dose for that day)

- Review the subject's diary and record changes in concomitant medication, deviations from drug schedule and adverse events.
- Vital Signs: Blood pressure, Pulse, and Temperature taken while subject is in a sitting position.
- Visual Acuity (Snellen's chart) with eye glasses (if applicable)
- OSDI
- Symptom Intensity Assessment, SGA and CGA
- Test Substance Tolerance (VAS)
- Keratograph Oculus Redness Score
- > Non-invasive Keratography Tear Film Break-up Time (NIK BUT)
- Schirmer I test
- Baseline Ophthalmic Examination (slit lamp examination, VBR)
- Ocular surface wash collection for analysis (Potential biomarkers)
- InflammDry Test for MMP-9 Protein
- Lissamine Dye Corneal and Conjunctival staining
- Intraocular pressure measurement after topical anesthesia to eye
- **Returning of unused study drug/ placebo (by patient to pharmacy)**

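### The Visit 2 and Week 8 lists print Schirmer and the 50 microlitre wash ahead of InflammaDry, contrary to Section 3.4.7 on Schirmer, and nothing protects the test from the wash

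*Combined protocol and SAP*

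**What the plan says.** Section 3.4.7 is the only place that sets an order for this test: "InflammaDry will be performed PRIOR to instilling ocular anesthetic, topical dyes, or performing Schirmer testing". The wash is not named there. The specimen is tear fluid: "Tear fluid sample will be collected by gently dabbing the sampling fleece on the inside of the patient's palpebral conjunctiva". The read-out is two-valued at a fixed threshold. A result line means 40 ng/ml or more, and otherwise "A negative result is indicative of an MMP-9 < 40 ng/ml".

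Section 3.6 schedules the wash at the same two visits: "At the first (Baseline) and last treatment (8 week) visits, ocular surface washings will be collected as follows". It uses 50 microlitres "of artificial tear (Preservative Free Refresh Optive Sensitive, Allergan, Irvine, CA) was instilled into the lower fornix of the eye". After eye movements and about one minute, fluid is drawn off with a 5 microlitre capillary. The volume recovered is not stated.

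In Section 6.5.2 (Day 1, pre-dose) the printed sequence is Schirmer I, slit-lamp examination, wash, "InflammADry Test for MMP-9 Protein", lissamine. Section 6.5.4 (Week 8) prints the same sequence, with "InflammDry Test for MMP-9 Protein" again directly below the wash and above lissamine.

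Change in MMP-9 detection is exploratory endpoint 14 in Section 3.4. Section 1.5 says the results of this study will guide the choice of primary or co-primary endpoints for later studies.

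**The concern.** There are two separate problems.

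- **A contradiction, on Schirmer only.** Section 3.4.7 puts InflammaDry before Schirmer. Both visit lists print it after.
- **An omission, on the wash.** Artificial tear is neither an anesthetic nor a dye, so Section 3.4.7 does not cover it. Someone who obeys that section to the letter can still wash the eye first, and both lists put the wash immediately before the test.

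The test reads the concentration of a protein in tear fluid against a fixed threshold. Added fluid lowers the concentration and leaves the threshold where it is. Eyes moderately above 40 ng/ml are the ones at risk of being called negative. Fewer positives at baseline leave less room to show a change at Week 8, and uneven timing between wash and test would add noise.

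The groups are small. With 12 per arm (Section 7.1), one misclassified target eye moves an arm's proportion by 1/12 = 8.3 percentage points.

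**Working it through.** **Step 1. Compare the rule with the lists.**

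| Procedure | Section 3.4.7 | Sections 6.5.2 and 6.5.4 as printed | Agreement |
|---|---|---|---|
| Anesthetic | after InflammaDry | after (intraocular pressure: post-dose on Day 1, after lissamine at Week 8) | yes |
| Dye (lissamine) | after InflammaDry | after | yes |
| Schirmer I | after InflammaDry | before | **no** |
| Wash, 50 microlitres | not mentioned | directly before | no rule exists |

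On Day 1, Schirmer is the 8th pre-dose item, the wash the 10th and InflammaDry the 11th. Section 3.6 gives no order or waiting time relative to InflammaDry.

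**Step 2. Illustrate the dilution.** The plan gives no dilution figure, so there is none to reproduce. From the documents come the 50 microlitres instilled and the 40 ng/ml cut-off. Two quantities have to be assumed:

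- V, the resident tear volume: 3 to 10 microlitres.
- r, the wash fluid still mixed with that tear at sampling: 5, 10 or 50 microlitres.

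With simple mixing:

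- dilution = (V + r) / V
- undiluted MMP-9 needed to read positive = 40 × (V + r) / V

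| r (microlitres) | V = 3 | V = 10 |
|---|---|---|
| 5 | 8/3 = 2.7-fold; 107 ng/ml | 15/10 = 1.5-fold; 60 ng/ml |
| 10 | 13/3 = 4.3-fold; 173 ng/ml | 20/10 = 2.0-fold; 80 ng/ml |
| 50 | 53/3 = 17.7-fold; 707 ng/ml | 60/10 = 6.0-fold; 240 ng/ml |

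An eye whose true value lies between 40 ng/ml and the figure in the cell would read negative.

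**Step 3. Repeat with the test done first.** Then r = 0, the dilution is V/V = 1, and the effective cut-off is 40 × 1 = 40 ng/ml whatever V is.

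**The case against.** **The lists are not stated to be in order of performance.** The opening of Section 6.5 says only that the procedures take place at the visit. Other parts of the protocol are plainly not chronological. The Week 4 list prints dispensing before return of unused drug, while Section 5.9.3 has the old droppers retrieved first. The schedule table prints lissamine above both the wash and InflammaDry. Section 3.4.7 is explicit and would normally prevail over an unordered list. This stands: the documents do not show that Schirmer will in fact be done first. It does not help with the wash. If the lists carry no order, the order of wash and test is simply uncontrolled.

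**Full retention is a worst case.** A reader might take 6- to 18-fold as the expected dilution. That requires all 50 microlitres to be present at sampling, although Section 3.6 has about a minute of eye movement followed by capillary collection. The objection stands, and the lower rows of the table belong in the range. Drawing off an already mixed fluid does not by itself restore the concentration; drainage before mixing and fresh tear do. The documents quantify neither.

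**Test order would not replace the drug effect.** A reader might infer that endpoint 14 would measure test order rather than treatment. The documents do not support that. The printed order is the same at both visits and in both masked, randomised arms, so the error should be broadly non-differential. One could argue that a treatment effect on tear volume would make dilution differ by arm, but nothing in the documents shows such an effect. Likewise, the documents give no direction or size for any influence of Schirmer on the MMP-9 result.

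**The stakes are low.** This is one of 15 exploratory endpoints, and Section 7.2 rules out efficacy tests. That is correct, and it limits the point to a minor one.

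**Conclusion.** The point holds as a minor inconsistency plus a gap. Section 3.4.7 and the lists in Sections 6.5.2 and 6.5.4 disagree on Schirmer, and no section keeps the wash away from InflammaDry.

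Residual wash fluid can turn true positives into negatives. The amount depends on two volumes that the documents do not give. Under simple mixing with 3 to 10 microlitres of resident tear, eyes up to about 60 to 107 ng/ml would read negative if 5 microlitres of wash remain, and up to about 240 to 707 ng/ml if all 50 remain.

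The likely consequence is fewer positives and a blunted or noisier change in endpoint 14. It is not an artefactual benefit or harm of the drug. The primary tolerability endpoint and the sample size are unaffected. The matter deserves correction because Section 1.5 intends these results to inform the endpoints of later studies.

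**What to change.** Three text changes:

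1. In Sections 6.5.2 and 6.5.4, list InflammaDry before Schirmer I and before the wash.
2. State in both sections that these tests are done in the listed order, at both visits.
3. In Section 3.4.7, add the ocular surface wash to the procedures that must come after InflammaDry.

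This adds no procedure or visit. There is one small trade-off: dabbing tear fluid first may slightly alter the wash specimen used for cytokines (endpoint 15). With a fixed order, that would apply equally in both arms and at both visits.

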3.4.8 Exploratory Efficacy End Point: Symptom (Ocular Discomfort) Intensity

Symptom (ocular discomfort) intensity will be assessed utilizing a Visual Analog Scale (VAS). The VAS is a horizontal line with verbal descriptor anchors at regular intervals. Symptom intensity will be

assessed on baseline, week 4, week 8, and week 10. Subjects will be asked to assess their symptom intensity as a fraction of 10. The symptom intensity will be assessed as follows:

Question to the patient: On a scale from 0-10, what was the intensity of your ocular discomfort, at its worst, over the past 24 hours?

3.5 Safety Endpoints

Safety assessments include Vital Signs, recording of all complications and adverse events, as well as ophthalmic exam findings. All ocular and non-ocular adverse events will be assessed for severity and relationship to the investigational product.

In addition to the primary tolerability endpoint (Section 2.2), the following safety endpoints will be assessed:

- The proportion of screened subjects who are successfully recruited in the study (i.e., recruitment rate)
- The proportion of eligible subjects at Day 56 who successfully complete (i.e., retention rate, (non)compliance or adherence rate) a full eight weeks (i.e., 56 days) of therapy with topical administration two times per day (BID).
- All reported adverse events, classified by frequency, severity, and relatedness, from baseline (Day 1) through the last study visit (Day 70).
- Clinically significant changes in vital signs or ophthalmic examination from baseline.

3.5.1 Vital Signs

Vital signs will be obtained and recorded at the Day 1 Visit, prior to the first administration of the test medication (placebo/ study drug) and week 4, week 8 and week 10. The following vital signs will be measured: 1) blood pressure measurements (mm Hg) will be taken while the subject is relaxed in a sitting position for at least 3 minutes with the arm at heart level. 2) Heart rate will be measured via auscultation of the heart or palpation of a peripheral pulse and will be recorded in beats per minute (bpm). 3) Oral temperature will be recorded in degrees Fahrenheit (⁰F). Subjects with an oral temperature less than (\leq) 99.6⁰F (37.4⁰C) may continue.

Clinically significant negative changes from baseline will be recorded on the adverse event forms.

3.5.2 Ophthalmic Examination

At all visits, the Investigator will conduct a complete undilated examination of the eyes using a binocular slit lamp. The Investigator will examine the tear film, eye lids, lashes, bulbar and palpebral conjunctiva, upper and lower lid puncta, cornea, anterior chamber, iris, lens, and anterior vitreous. Specific signs (if they are present) that will be recorded include: lacrimal sac area erythema, swelling or tenderness; froth or debris or mucous strands in tear film; eyelid hyperemia; punctal hyperemia or atresia; conjunctival/ episcleral hyperemia; papillary or follicular conjunctival reaction; chemosis, episcleral edema; superficial punctate keratopathy, corneal scar, corneal neovascularization; presence and

number of corneal filaments, presence or absence of mucoid films, anterior chamber cell, flare or KPs; pupil shape abnormalities, anterior or posterior synechiae, iris neovascularization; lenticular opacities; vitreous cells or pigment. Conjunctival hyperemia (ocular surface redness) will be graded at each visit using the VBR grading system as explained in section 3.4.5. Measurements at first and last visit will include: visual acuity (Snellen's chart), manifest refraction and intraocular pressure measurement. Clinically significant changes from baseline examination will be recorded on the adverse event forms. Corneal filaments are mucous tags that are adherent to the surface of cornea. Mucoid films are mucous collections accumulating on the surface of the eye. The number of such mucus tags/ filaments will be counted on each clinical examination (slit-lamp examination).

3.6 Other Study procedures: Ocular Surface Washings

At the first (Baseline) and last treatment (8 week) visits, ocular surface washings will be collected as follows: 50 μ L of artificial tear (Preservative Free Refresh Optive Sensitive, Allergan, Irvine, CA) was instilled into the lower fornix of the eye. The patient will be instructed to perform ductions in all directions, and after approximately 1 minute the conjunctival washings were collected with a 5 μ L glass microcapillary tube (Microcaps Drummond Scientific, Broomall, PA) and transferred to a sterile 0.2 mL microcentrifuge tube. The samples will be stored at cold temperature (approximately 4 degrees C) until further analysis. Ocular Surface washings will be transported to the laboratory and used for potential biomarker analysis etc.

4 Subject Selection and Withdrawal

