3.1 General Design

This will be a Randomized controlled trial, in which a total of 28 subjects will be enrolled at 1 clinical site. Subjects will be randomly assigned to one of two groups (#1, #2), with 14 subjects per group. One group will be given placebo (Normal saline eye drops) and the other group will be given eye drops containing the study drug (IVIG).

Patients with established Dry Eye Disease will be approached by a member of the research staff to determine if he/ she might be interested in participating in a research study. If the subject is interested, the research staff member will describe the study. If the subject is willing to enter the study, the study will be discussed and the subject will be asked to sign the informed consent form. Consent will be obtained prior to screening to determine eligibility. Screening procedures include documentation of Dry Eye Disease. Eligible subjects will be enrolled in the study.

All enrolled subjects will receive their first dose of test medication (placebo/ study drug) on study Day 1 in the doctor's office, and after completion of the study assessments, will have the topical eye drops dispensed for self-administration. See Section 5.4 *Preparation and Administration of Study Drug* for details.

Subjects will be provided with diaries to record the time of each dose and will also be asked to record any adverse symptoms. In addition, they will be asked to make a note of any missed doses together with the reason for the omission. Subjects will return at 4 weeks for further study assessments,

thereafter at 8 weeks (the last day of treatment), and again at 10 weeks after two weeks of no treatment with study drug for the final study assessments.

There is no primary efficacy endpoint in this study. Instead several exploratory efficacy endpoints will be assessed.

The primary tolerability endpoint is the change in the test substance tolerance between Day 1 (post-dose) and 8 weeks (56 days).

[figure not shown]

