3.4 Exploratory Study Endpoints

The exploratory study endpoints will include:

1. The change in the Ocular Surface Disease Index (OSDI) which is a patient’s subjective rating scale
2. Change in tear secretion as measured by Schirmer I test
3. The proportion of eyes achieving complete corneal staining clearance after treatment
4. Change in corneal staining score as measured by Lissamine dye staining

[figure not shown]
5. The change in subjective ocular surface redness score (OR) using the validated bulbar redness (VBR) grading scale
6. Visual acuity change
7. Change in frequency of administration of artificial tears or concomitant eye drops
8. Change in number of corneal filaments (slit-lamp examination)
9. Change in amount of mucoid films (slit-lamp examination)
10. Clinical Global Impression (CGI) of change in symptoms from baseline (physician's rating)
11. Subject Global Assessment (SGA) of overall change from baseline (subject's rating)
12. Change in Non-Invasive Keratograph Tear Break-Up Time (NIK BUT)
13. Change in Keratograph Ocular Bulbar Redness Score
14. Change in MMP-9 Protein Detection
15. Change in amount of Cytokines in ocular surface wash

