7.1 Sample Size Determination

As this is a feasibility trial intended to guide the planning of larger future investigations, there are no formal sample size calculations.⁶⁵ The aim of the study is to recruit a sufficient number of patients to evaluate the acceptability and safety of the intervention and the study design. An outcome of this study will be to estimate parameters such as the SD for a sample size calculation of a subsequent full-scale trial. A sample of 24 patients (12 in each arm) is considered adequate for obtaining reliable sample size estimates.^{66, 67} To allow for a conservative attrition rate of 10%, we aim to recruit 28 patients into the trial.

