7.2 Statistical Methods

Based on the classification of reasons for conducting pilot studies by Thabane et al, in this pilot study we will assess the following: (i) Process– recruitment rate, retention rate, (non)compliance or adherence rate; and (ii) Scientific– safety (adverse event/SAE rate), tolerability, and efficacy, including reduction in clinical signs and symptoms (OSDI, Corneal staining, Redness etc as detailed in section 3.4) and treatment effect size. We will calculate the observed rate with 95% confidence interval for each rate by treatment group. Other descriptive statistics, including median with interquartile or mean with standard deviation for continuous variables and frequency with percentage for categorical variables will be reported as well. To estimate the preliminary efficacy under the scientific category, one eye (target eye) will be selected at screening visit as follows: (i) if only 1 eye meets inclusion criteria, this eye is used; (ii) if both eyes meet inclusion criteria, the eye with the higher corneal stain score is used; (iii) if both eyes have the same corneal stain score, then the one with the lower Schirmer I score is used; (iv) if both eyes have same scores, the right eye is used. Secondary analyses will be performed for the non-target eye as well. Due to the nature of this feasibility study, any efficacy statistical tests and adjusted analyses will not be conducted. Detailed data validation will examine completeness, existence and accuracy of collected data to assess data quality and identify missing and conflicting data. Statistical analysis will be performed on an intention-to-treat basis i.e., inclusion of all patients randomly assigned, regardless of adherence, actual treatment received, and subsequent withdrawal of treatment and/or deviation from the protocol and per-protocol (i.e., inclusion of those who completed the treatment as planned) and will be reported according to 2010 CONSORT guidelines. All statistical analyses will be completed using SPSS Statistics V.22.0.31

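### Washes for the cytokine endpoint are kept at about 4 degrees C with no time limit, freezing step or paired-assay rule, so storage age or assay run can distort the within-arm change

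*Combined protocol and SAP*

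**What the plan says.** Section 3.4, item 15, lists as an exploratory endpoint "Change in amount of Cytokines in ocular surface wash".

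Section 3.6 sets the sampling: "At the first (Baseline) and last treatment (8 week) visits, ocular surface washings will be collected as follows". The visit schedule and sections 6.5.2 and 6.5.4 agree that Day 1 (before dosing) and Week 8 are the only two collections. Section 6.5.4 allows the Week 8 visit to move by 4 days either way.

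On storage, section 3.6 says: "The samples will be stored at cold temperature (approximately 4 degrees C) until further analysis". On use, it adds: "Ocular Surface washings will be transported to the laboratory and used for potential biomarker analysis etc".

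The text supplied states no maximum storage time, freezing step, stability data, assay date or rule about which samples share an assay run.

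Section 7.2 plans descriptive statistics and a treatment effect size, and states that "any efficacy statistical tests and adjusted analyses will not be conducted".

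**The concern.** A change score is sound only if both measurements are made under the same conditions. Here the storage rule ends at an undated event, so the two samples that form each change may differ in age by the whole treatment period.

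Any protein lost in cold storage would then fall more heavily on the baseline sample. Baseline would read low, and the change would shift upward. A real fall in cytokines, which is what an anti-inflammatory treatment would be hoped to show, could be masked or reversed.

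The documents give some reason to take loss seriously. Section 1.3 names matrix metalloproteinases in the disease response. Section 1.7 (Figure 6) reports elastase-positive neutrophils, described as activated, on the ocular surface in Sjogren's dry eye. This makes degradation in an unfrozen wash plausible, but gives no rate.

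Endpoint 15 is also the only quantitative molecular endpoint, because section 3.4.7 describes the MMP-9 test as qualitative. The washes are small, are taken only twice, and cannot be repeated once they have aged.

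**Working it through.** The plan gives no figure on storage loss, so there is none to reproduce. Its recruitment target of 28 does not enter this point.

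**Inputs**
- Collection at Day 1 and Week 8 (3.6); Week 8 is 56 days, with a window of 4 days either way (6.5.4).
- Age gap within a pair if both samples are assayed in one run: 56 − 4 = 52 to 56 + 4 = 60 days.
- Loss rate at about 4 degrees C: not in the documents. Assumed range 0 to 1% per day, first order, rate k.
- Timing of assay: not in the documents, so both cases are worked.

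**Case A: each pair assayed together**

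Baseline fraction remaining relative to Week 8 = exp(−k × d), where d is the age gap in days. Apparent Week 8/baseline ratio = true ratio × exp(k × d).

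| Loss per day | Baseline remaining, d = 56 | Apparent ratio, no true change | Same, d = 52 to 60 | A true ratio of 0.70 reads |
|---|---|---|---|---|
| 0 | 1.000 | 1.00 | 1.00 | 0.70 |
| 0.2% | exp(−0.112) = 0.894 | 1.12 | 1.11 to 1.13 | 0.78 |
| 0.5% | exp(−0.28) = 0.756 | 1.32 | 1.30 to 1.35 | 0.93 |
| 1% | exp(−0.56) = 0.571 | 1.75 | 1.68 to 1.82 | 1.23 |

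At 0.5% per day, a true ratio of 0.756 (a 24% fall) would read as no change. The true ratio of 0.70 is illustrative only.

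A second grid, with loss stated per week over 8 weeks, gives the same picture. The apparent ratio is 1/(1 − w)^8: 1.00 at zero loss, 1.08 at 1%, 1.51 at 5% and 2.32 at 10% per week.

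**Between arms, case A.** Both arms follow the same procedure. If the true ratios are R1 (IVIG) and R0 (placebo), the observed ratio of ratios is [R1 × exp(k × d)] / [R0 × exp(k × d)] = R1/R0. With R1 = 0.70 and R0 = 1.00 at 0.5% per day, this is 0.93/1.32 = 0.70, the true value.

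**Spread between subjects, case A.** On the log scale the artefact is k × d. If all samples are run on one date at study end, d is 52 to 60 days for every pair, whatever the enrolment date. At 0.5% per day, k × d runs from 0.26 to 0.30, a span of 0.04, or about 4% in the ratio (exp(0.04) = 1.04).

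**Case B: each sample assayed soon after its visit.** The age gap is about 0, so the storage factor is exp(0) = 1.00. The two samples then come from different assay runs, and each change carries a factor (run effect at Week 8)/(run effect at baseline). The documents give nothing from which to size it.

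**The case against.** **The 4 degree hold may be short.** The sentence after the storage rule sends the washes to the laboratory, so the cold hold may be only a brief step before transfer and prompt assay. Batching is nowhere stated, and zero loss or prompt assay gives no storage artefact. This stands, and it is why the point is conditional. A reader might infer that a one-way error is built into the endpoint. The documents do not show that; they show a rule that permits one. Prompt assay does not settle the matter either, because it splits each pair across runs.

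**The placebo arm protects the comparison.** This largely stands: a common proportional loss leaves the IVIG-to-placebo ratio unchanged. A reader might infer that the treatment contrast is biased, and that does not follow. Two smaller routes remain. If Week 8 samples also age before assay, absolute between-arm differences shrink: 180 days at an assumed 0.5% per day leaves exp(−0.9) = 0.41 of the difference. Residual IgG in Week 8 washes could also alter stability in one arm only, which is possible but not shown.

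**The SD for the next trial.** A reader might infer that unequal hold times inflate the SD that section 7.1 hopes to supply. The documents do not support this. On the ratio scale, enrolment order drops out when all pairs are run on one date. On the absolute scale, longer storage shrinks values, so inflation cannot be presumed. Section 7.1 does not name cytokines, and section 1.5 expects a sign or symptom to become the later primary endpoint.

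**It is a minor endpoint.** Cytokines are the last of 15 exploratory endpoints, and no efficacy tests are planned. This stands and limits the weight of the point. But with no testing or adjustment, the descriptive change is the result itself, and nothing downstream would correct it. Handling detail could sit in a laboratory manual, but section 3.6 neither cites one nor bounds the hold.

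**Conclusion.** The point holds in a conditional form. Section 3.6 permits an age gap of 52 to 60 days between the two samples behind endpoint 15. If pairs are assayed together and cytokines are lost at about 4 degrees C, the within-arm Week 8/baseline ratio is biased upward. The bias factor is 1.00 at zero loss, and 1.12, 1.32 or 1.75 at 0.2%, 0.5% or 1% per day. If samples are assayed separately and promptly, the storage bias goes and run-to-run variation of unknown size replaces it.

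The figures rest on three assumptions that the documents neither state nor exclude: same-run assay, first-order loss, and the loss rates themselves. The risk lies mainly in the within-arm summaries. The IVIG-to-placebo ratio is largely protected, and the primary tolerability and safety endpoints are unaffected. The change is still worth making before the first sample is taken, because storage loss cannot be undone and the remedy is cheap.

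**What to change.** Replace the storage sentence in section 3.6 with a rule that does four things:

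1. Freeze each wash promptly after collection, for example the same day at −70 degrees C or colder, or in another condition that the laboratory's own stability data support.
2. Record collection and freezing times for every sample.
3. Assay each subject's Day 1 and Week 8 samples in the same run.
4. Flag any sample held unfrozen beyond the laboratory's stated limit, and report endpoint 15 with and without flagged samples. Excluding them outright would cost data in a trial of this size.

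The cost is one paragraph and freezer space, plus a delay in assaying baseline samples until the Week 8 sample is in hand. No extra visit or sample is needed, and the sample size does not change.
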